4.1.2 Crossover

At investigator-assessed PD per RECIST 1.1, treatment allocation will be unblinded and those patients randomised to the savolitinib plus placebo arm will have the opportunity to cross over to the savolitinib plus osimertinib regimen. Patients will be informed of the possibility of crossover to savolitinib plus osimertinib during the initial informed consent process and at the

time of progression on randomised treatment. A separate informed consent form (ICF) for crossover patients must be signed prior to starting crossover treatment.

Patients who cross over must not receive any other anti-cancer therapies between the initial assessment of PD and the addition of osimertinib. Savolitinib treatment should continue uninterrupted during this period. Patients should be crossed over as soon as possible after the assessment of PD and within 28 days of their progression scan.

Patients who cross over will receive study medication once daily in 28-day cycles until objective PD by RECIST 1.1 is assessed by investigator, unacceptable toxicity occurs, consent is withdrawn or another discontinuation criterion is met. As in the treatment allocation/randomisation part of the study, patients may continue to receive treatment with osimertinib plus savolitinib or osimertinib monotherapy (if savolitinib is stopped during cross over because of savolitinib-related toxicity) beyond RECIST 1.1 defined PD as long as they continue to receive clinical benefit, in the opinion of the investigator, and do not meet any of the discontinuation criteria. No other anti-cancer agent is permitted in combination with osimertinib within this study.

If, after the planned futility analysis the savolitinib + placebo arm is declared futile, all patients remaining on savolitinib + placebo will be contacted and asked to return for a discussion of the futility findings and their options for remaining in the savolitinib + placebo arm (as long as, in the opinion of the investigator, they are still receiving clinical benefit and have not reported PD) or crossing over to the savolitinib + osimertinib arm. Patients who cross over must not receive any other intervening anti-cancer therapies before the addition of osimertinib.

All patients who cross over to receive savolitinib + osimertinib (whether based on objective PD by RECIST 1.1 or a declaration of futility of the savolitinib + placebo arm) will follow the scheduled procedures described in [Table 2](#).

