- c The frequency of liver function tests will depend on the timepoint at which the patient crosses over. Liver function tests should be performed weekly for the first 10 weeks of the study (ie, for patients who cross over prior to completing 10 weeks of the study) then on Day 1 of every subsequent cycle in the crossover period. Where a liver function test is the only assessment, a clinic visit is not required as the test may be performed offsite. In the case of elevated liver function tests, please refer to Appendix I 3.3 for enhanced monitoring and management procedures.
- f At all visits, [REDACTED] mL blood for plasma is required for ctDNA to measure clearance of EGFR mutation alleles and for exploratory analysis.
- g **CCI** [REDACTED] for savolitinib and is optional.
- h For patients who cross over based on confirmed objective disease progression during the initial randomised treatment period, scheduled RECIST 1.1 tumour assessments are not required, and the subsequent assessment of disease progression will be based on standard-of-care scan or investigator determined clinical progression. Scheduled RECIST 1.1 tumour assessments are required (the scan frequency is against initial randomisation) for patients who cross over based on a declaration of futility of the savolitinib monotherapy arm and who have not objectively progressed during the initial randomised treatment period. Patients who cross over based on a declaration of futility, who have no objective progression during initial randomisation period, and who discontinue study drug after cross-over for reasons other than investigator-confirmed disease progression will continue scheduled RECIST 1.1 tumour assessments until objective disease progression per RECIST 1.1 as assessed by investigator, unless they withdraw consent to the entire study. At the same time points, vital signs, and ECGs will be collected. SAEs considered related to study treatment and/or study procedures will be collected throughout progression follow-up.
- i Patients who cross over must not receive any other anti-cancer therapies between the assessment of PD and the addition of osimertinib. Savolitinib treatment should continue uninterrupted during this period.

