80 mg od arm. Under CSP version 7.0, patients must have confirmation of MET-amplified/overexpressed (FISH10+ and/or IHC90+) tumour status by FISH (central) and IHC (central) testing. Pre-existing next generation sequencing testing results are not accepted to enter Screening.

Intervention duration

All patients confirmed as eligible will begin treatment on Day 1 with osimertinib + savolitinib combination therapy or placebo to osimertinib + savolitinib. Treatment will continue in 28-day cycles until either objective disease progression by investigator per RECIST 1.1 is assessed, unacceptable toxicity occurs, consent is withdrawn or another discontinuation criterion is met.

Patients randomised to the placebo + savolitinib 300 mg bid arm may cross over to osimertinib 80 mg od + savolitinib 300 mg bid following investigator-assessed PD per RECIST 1.1.

Independent data monitoring committees

An independent data monitoring committee will meet to assess the futility of the savolitinib 300 mg bid + placebo arm after **CC1** patients have been randomised under CSP version 7.0 and have had an opportunity to have 2 post-baseline scans. The IDMC will also review at this time the safety data of the randomised patients recruited under CSP version 7.0 for both arms (Appendix A 5). More details are provided in the IDMC charter.

In addition, **CC1**

Statistical considerations:

The study will have 5 planned analyses. Interim Analysis 1 was planned and performed after approximately **CC1** patients treated with osimertinib and 300 mg od savolitinib had the opportunity to be treated for 2 post-baseline Response Evaluation Criteria in Solid Tumour (RECIST) scans (12 weeks) or the **CC1** patient treated with osimertinib (80 mg od) and savolitinib (300 mg od) had the opportunity to be treated for 6 weeks, whichever was later. Continuous monitoring of the discontinuation due to adverse event (AE) rate and the discontinuation due to a hypersensitivity/anaphylaxis AE rate was to be performed after the **CC1** patient treated with osimertinib and 300 mg od savolitinib had the opportunity to be treated for 6 weeks up to the first interim analysis.

Interim Analysis 2 was planned and performed after approximately CC1 patients treated with osimertinib (80 mg od) and savolitinib (300 mg od) in the second line setting had the opportunity to be treated for 2 post-baseline scans (12 weeks).

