6 STUDY INTERVENTION

Study treatment is defined as any IP(s) (including marketed product comparator and placebo) or medical device(s) intended to be administered to a study participant according to the study protocol. Study treatment in this study refers to osimertinib and/or savolitinib.

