Patients randomised to the savolitinib 300 mg bid + placebo arm may cross over to savolitinib 300 mg bid plus osimertinib 80 mg od following investigator assessment of PD per RECIST 1.1. Once the investigator has documented progression in the eCRF, and obtained approval for unblinding from the study physician, the treatment code for a patient may be obtained from the IWRS via a dedicated option they may select in this situation. In all other circumstances the treatment code should not be unblinded except in medical emergencies when the appropriate management of the patient requires knowledge of the treatment allocation. The investigator documents and reports the action to the AstraZeneca study physician, without involvement of other personnel to maintain study integrity.

AstraZeneca retains the right to break the code for SAEs that are unexpected and are suspected to be causally related to an investigational product and that potentially require expedited reporting to regulatory authorities.

Treatment codes will not be unblinded for the planned analyses of data until all decisions on the evaluability of the data from each individual patient have been made and documented.

The IWRS will be programmed with blind-breaking instructions. In case of an emergency, in which the knowledge of the specific blinded study intervention will affect the immediate management of the patient's condition (eg, antidote available), the investigator has the sole responsibility for determining if unblinding of a patients' treatment assignment is warranted. Patient safety must always be the first consideration in making such a determination. If a patient's treatment assignment is unblinded, the sponsor must be notified within 24 hours after

breaking the blind. The investigator documents and reports the action to the AstraZeneca physician, without involvement of other personnel to maintain study integrity. Additionally, patients with investigator-assessed objective PD may be unblinded.

The personnel analysing the PK samples will be unblinded to the investigational treatment for each patient.

The AstraZeneca study team will be unblinded at the time of the primary analysis. Site staff and patients will remain blinded until database lock for the final analysis.

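### Protocol section 4.1.2 has crossover patients take study medication once daily, while the crossover regimen elsewhere includes savolitinib 300 mg bid; the passages must be reconciled

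*Protocol*

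**What the plan says.** Protocol section 4.1.2 (Crossover) gives the instruction: "Patients who cross over will receive study medication once daily in 28-day cycles". The sentence continues with the end of treatment, "until objective PD by RECIST 1.1 is assessed by investigator", and then adds toxicity, withdrawal of consent and any other discontinuation criterion. The section states no savolitinib dose in milligrams.

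Elsewhere the crossover regimen carries both dose and frequency:

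- Synopsis, intervention duration: "Patients randomised to the placebo + savolitinib 300 mg bid arm may cross over to osimertinib 80 mg od + savolitinib 300 mg bid". The synopsis paragraph on patient numbers says the same.
- Section 6.3: "Patients randomised to the savolitinib 300 mg bid + placebo arm may cross over to savolitinib 300 mg bid plus osimertinib 80 mg od".
- Section 4.1.1 and section 8.1.1 (for both the PD and the futility route) also pair savolitinib 300 mg bid with osimertinib 80 mg od. The opening of section 1.1 gives savolitinib 300 mg bid plus osimertinib.

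On imaging, Table 2 footnote h says that for patients who cross over on confirmed objective progression, "scheduled RECIST 1.1 tumour assessments are not required". Later progression is then judged from routine-care scans or clinically by the investigator. SAP section 3.2.1.1.1 repeats this. Protocol section 8.1.1 likewise says that scheduled imaging is not required on that route.

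**The concern.** Section 4.1.2 is where a site would look for how a crossover patient is treated, and its wording tells the site how often to give the drugs. It conflicts with the regimen stated elsewhere. The randomised-phase sentence in section 4.1.1 mentions 28-day cycles but no frequency, so the once-daily wording is specific to the crossover instruction.

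Several other rules depend on the frequency:

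- Table 6 sets the missed-dose window at 12 hours for once-daily savolitinib and 6 hours for twice-daily.
- Section 8.4.3 defines an overdose as exceeding the protocol-defined daily dose and requires a report within 24 hours. That needs one defined daily dose.
- SAP section 3.2.2.2 computes relative dose intensity against the intended cumulative dose. If post-crossover dosing is summarised, the denominator depends on which frequency was intended.

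Protocol section 9.4.3.2 also says the impact of crossover on OS may need to be assessed. Interpreting that would require a clear post-crossover regimen.

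The second, smaller issue is that, for the PD route, one of the named stopping criteria is an objective assessment that the crossover schedule does not require.

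**Working it through.** The documents state no figure for this point, so there is nothing to reproduce. The check sets the passages side by side, followed by one line of arithmetic.

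**Step 1. Does the once-daily wording cover savolitinib?** Section 6 says "Study treatment in this study refers to osimertinib and/or savolitinib". Section 4.1.2 uses the term study medication, which section 6 does not define in those words. Covering both drugs is the natural reading, because the patient is taking both, but the definition does not strictly prove it.

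**Step 2. Does anything nearby settle the frequency?**

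| Place | Savolitinib frequency after crossover |
|---|---|
| Section 4.1.2 | once daily, no mg amount |
| Synopsis; sections 1.1, 4.1.1, 6.3, 8.1.1 | 300 mg bid |
| Table 2, treatment rows | daily dosing for both drugs; number of doses per day not given |
| Table 6 | lists 300 mg once daily, 600 mg once daily and 300 mg twice daily |

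Table 2 fits either reading. Table 6 contains both frequencies and does not say which applies to crossover. Section 4.1.2 also asks for savolitinib to continue without a break, but that covers the interval between PD and the addition of osimertinib, not the crossover period itself.

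**Step 3. Size, under stated assumptions.** Section 4.1.2 gives a frequency only, so a milligram amount has to be assumed from Table 6.

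- Regimen stated elsewhere: 300 mg × 2 = 600 mg/day.
- Once daily, assumed 300 mg: 300 mg × 1 = 300 mg/day. Ratio 300/600 = 0.5, a 50% difference.
- Once daily, assumed 600 mg: 600 mg × 1 = 600 mg/day. Difference 600 − 600 = 0 mg/day; only the frequency differs.

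The range is therefore from no difference in daily amount to half.

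**Step 4. Do the primary analyses depend on this?** The two primary ORR analyses use the TPAS (patients assigned to savolitinib 300 mg bid + osimertinib) and the SAF patients on savolitinib 300 mg od + osimertinib. Analyses are presented by assigned starting regimen, and SAP section 2.2 keeps crossover patients under their initial allocation. Patients randomised to savolitinib + placebo therefore enter neither. For the PD route, investigator-assessed ORR and PFS are already determined by the progression that triggers crossover. SAP section 3.1.1 also cuts off savolitinib + placebo assessments before the first combination dose.

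**Step 5. Stopping criterion, by route.**

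| Route | Section 4.1.2 | Scheduled RECIST assessments after crossover |
|---|---|---|
| PD | RECIST 1.1 PD is one criterion | not required; routine-care scan or clinical progression |
| Futility, no objective PD | same sentence | required, timed from randomisation |

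The mismatch exists only in the first row.

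**The case against.** The strongest reply is that one phrase stands against a regimen stated consistently in five other places. Section 4.1.2 sits within the overall design, and the end of section 4.1.1 sends readers to section 6.1 for treatment details, so section 4.1.2 does not alone govern crossover dosing. Patients reach crossover already on 300 mg bid, crossover is described as adding osimertinib, and no passage orders a change in savolitinib. Many sites would probably keep to the regimen stated elsewhere. All of this stands and limits the likely consequence. It does not remove the contradiction, because section 6.1 leads to Table 6, which holds both frequencies.

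A reader might infer that section 4.1.2 halves the daily savolitinib dose. The text does not support that: it gives no amount, and the 300 mg/day figure is one assumption among those Table 6 allows. A reader might also infer that exposure and safety will differ between sites. That is possible, but it requires some sites to set aside the regimen given elsewhere, and nothing in the documents shows that they would.

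On progression, a reader might infer that scans are not done after PD crossover and that the stopping rule cannot be applied. The documents say only that scheduled assessments are not required. Routine-care scans are foreseen, and nothing bars the investigator from reading them by RECIST. RECIST PD is also not the sole stopping point: the same sentence lists other criteria, and the next allows treatment beyond PD while clinical benefit continues. The section then refers to Table 2, whose footnote h says how later progression is judged. What remains is a general sentence that does not distinguish the two routes.

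**Conclusion.** The inconsistency is real: a once-daily instruction in section 4.1.2 against a twice-daily savolitinib regimen in the synopsis and sections 1.1, 4.1.1, 6.3 and 8.1.1, with neither Table 2 nor Table 6 resolving it. The wording covers every patient who crosses over. Its size in daily savolitinib ranges from no difference to 300 against 600 mg/day, depending on an amount the section does not state. The conclusion rests on reading study medication as including savolitinib, which is natural but not defined in those exact words. What could be affected is operational and descriptive: the missed-dose window, overdose reporting and any post-crossover dose intensity. The primary ORR results are not affected.

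The progression wording is a secondary and smaller mismatch, confined to patients who cross over at PD. Both are faults of wording rather than of design.

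**What to change.** Reconcile the frequency wording in section 4.1.2 with the crossover regimen stated in the synopsis and sections 1.1, 4.1.1, 6.3 and 8.1.1, and make the savolitinib entry in Table 2 explicit so that it agrees. Align the progression wording in section 4.1.2 with Table 2 footnote h, stated separately for the PD route and the futility route. The clinical team decides which schedule and which progression rule apply; this review takes no position on either. If post-crossover dosing is to enter relative dose intensity, SAP section 3.2.2.2 should take its intended dose from the reconciled text. The cost is protocol wording only: no change to sample size, endpoints or primary analyses.

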4.2 Scientific rationale for study design

Refer to Sections [2](#) and [2.1](#).

4.2.1 Rationale for study design

The expansion cohort Part B of the TATTON study has demonstrated anti-tumour activity of osimertinib in combination with savolitinib (ORR 28%) in MET-amplified patients (confirmed centrally by FISH; MET gene copy ≥ 5 or MET/CEP7 ratio ≥ 2) who were treated with prior 3rd generation T790M-directed EGFR-TKI ([Ahn et al 2017](#)).

This Phase II study has been designed to further assess the efficacy of osimertinib in combination with savolitinib by assessment of ORR in patients with EGFRm+ and

MET-amplified/overexpressed, locally advanced or metastatic NSCLC who have progressed following treatment with osimertinib. Overall, this study will enrol patients who have received up to 3 lines of prior therapy which must include osimertinib but could also include other EGFR-TKIs, chemotherapy or chemotherapy in combination with an immuno-oncologic agent. For savolitinib 300 mg bid or 600 mg od in combination with osimertinib 80 mg od under CSP version 5.0, patients must have documented radiologic disease progression following treatment with 1L or 2L osimertinib as the most recent anti-cancer therapy (ie, up to 2 lines of prior therapy); chemotherapy and/or immunotherapy in metastatic setting will not be allowed. This is to reduce heterogeneity of the patient population and more closely match the proposed target population in the planned phase 3 study. Furthermore, patients enrolled to savolitinib 300 mg bid or 600 mg od in combination with osimertinib 80 mg od under CSP version 6.0, must have documented radiologic disease progression on 1L osimertinib and must have confirmed MET amplification by central FISH (FISH5+).

Emerging pre-clinical data (see Section 2) has suggested that savolitinib monotherapy may have anti-tumour activities in EGFRm NSCLC patients with higher MET amplification/overexpression. In order to describe the difference in efficacy of savolitinib in combination with osimertinib and savolitinib monotherapy in the treatment of patients with MET amplification/overexpression (FISH10+ and/or IHC90+) in EGFRm NSCLC with resistance to osimertinib, a savolitinib 300 mg bid + placebo arm has been included in the study design. Patients will be randomised in a double-blind manner to receive either savolitinib 300 mg bid + osimertinib or savolitinib 300 mg bid + placebo in order to minimise the assessment bias.

The objective response to platinum-pemetrexed chemotherapy has been consistent in NSCLC population (approximately ORR **CC1**%) and will be used as external reference (and thus is not included in the SAVANNAH study) when determining the efficacy of savolitinib + osimertinib in EGFRm MET amplified/overexpressed NSCLC.

To address clinical concern about the potential for tumour flare with the withdrawal of EGFR-TKI cover in an EGFRm driven indication, all patients will be closely monitored over the first month on study to look for evidence of tumour flare. This study also includes the option for patients randomised to the savolitinib plus placebo arm to cross over to receive savolitinib in combination with osimertinib upon investigator-assessed objective PD per RECIST 1.1.

Brain metastases are detected in 20% to 30% of patients with advanced NSCLC upon initial diagnosis and are associated with a poor prognosis (Porta et al 2011). The central nervous system is a common site of first progression for patients receiving treatment with TKIs, despite concomitant systemic disease control. The randomisation under CSP version 7.0 will

be stratified by brain metastasis at baseline to account for potential impact due to imbalance of patients with brain metastasis across arms.

4.2.2 Rationale for endpoints

ORR, PFS, duration of response (DoR) and percentage change from baseline in tumour size assessed by RECIST 1.1 using investigator assessment and OS are standard measures of clinical activity and are used to assess efficacy in solid tumour clinical studies.

The Phase 1 TATTON study data indicated encouraging anti-tumour activity in patients with centrally-confirmed MET-amplified status. Responses were also observed in a small number of MET overexpressed tumours by IHC without centrally-confirmed MET-amplification by FISH. In SAVANNAH, the primary endpoint to assess the ORR in patients treated at the 300 mg od savolitinib dose level, in combination with 80 mg od osimertinib, and whose tumours are FISH5+ and/or IHC50+ and had disease progression following prior osimertinib therapy was based on the TATTON study data.

Under CSP version 7.0, an additional primary endpoint has been added to evaluate the efficacy at an alternative savolitinib dose and using a higher biomarker cut-off for MET amplification and/or overexpression. Emerging clinical data (including from the TATTON study and SAVANNAH study) and published literature support a biological rationale for the apparent association of increasing MET overexpression or amplification levels with improvement in responses to MET inhibitors in EGFRm+ NSCLC patients with MET amplification and/or overexpression. Therefore, an additional primary endpoint will determine the ORR in patients treated at the 300 mg bid savolitinib dose level in combination with 80 mg od osimertinib, and whose tumours are FISH10+ and/or IHC90+ and have progressed following treatment with 1L osimertinib.

Secondary endpoints include, but are not limited to, assessment of efficacy parameters by varying savolitinib dose levels in combination with 80 mg od osimertinib and varying MET FISH and IHC cut-offs in order to allow a thorough assessment of dose-response relationships. A description of the difference in response rate between the 300 mg bid savolitinib + 80 mg od osimertinib group and the 300 mg bid savolitinib + placebo group as well as an exploration of the prevalence of plasma ctDNA clearance after 6 weeks of study therapy are also secondary objectives of this study.

The secondary symptoms and overall HRQoL endpoints, assessed using the European Organisation for Research and Treatment of Cancer (EORTC) 30-item core quality-of-life questionnaire (QLQ-C30), version 3 (QLQ-C30 v3) and the complementary 13-item lung cancer symptoms questionnaire (QLQ-LC13), will show the overall influence of the benefits and toxicity of the treatment from the patient's perspective and will aid in understanding the

benefit/risk evaluation. These PRO questionnaires are well-established instruments that have been previously included in cancer clinical studies.

Standard safety parameters (discontinuation rate due to AEs/SAEs, vital signs, clinical chemistry/haematology parameters and electrocardiograms [ECGs]) will be used to assess the safety and tolerability of osimertinib in combination with savolitinib. To evaluate the safety and tolerability of savolitinib in combination with osimertinib, the proportion of patients discontinuing due to any AE and the proportion of patients discontinuing due to AE of hypersensitivity/anaphylaxis may be assessed.

Standard PK parameters will be used to evaluate the PK of osimertinib and savolitinib when administered in combination in this population.

Exploratory endpoints, including, but not limited to, circulating tumour deoxyribonucleic acid (ctDNA), circulating proteins and germline deoxyribonucleic acid (DNA), will be used to understand mechanisms of response (where response is defined broadly to include biomarker change, tolerability or safety) and resistance to treatment.

